### 3.3.2 INCLUSION OF CHILDREN

This study will not include children or adolescents as the safety profile of xisomab 3G3 has not been evaluated in a pediatric population.

## 3.4 REGISTRATION PROCEDURES

### 3.4.1.1 OHSU Registration

Participants will be required to give written informed consent to participate in the study before

any screening tests or evaluations are conducted that are not part of standard care.

Registration from all consented participants must be entered into the OHSU electronic Clinical Research Management System (CRMS, e.g., eCRIS). At a minimum, registration of OHSU participants will include signed copies of the most recently IRB-approved, informed consent form and HIPAA authorization.

### **3.5 PARTICIPANT SCREENING AND ENROLLMENT**

In order to participate in this study, signed informed consent must be obtained from the participant or the participant's legally acceptable representative. The current Institutional Review Board (IRB) approved informed consent must be signed and dated by each participant prior to undergoing any study procedures or before any prohibited medications are withheld from the participant in order to participate in this study.

Screening will begin once the participant has provided written informed consent to participate in the study . All screening and baseline evaluations will be performed during the screening phase (i.e., up to 28 days before catheter placement). Day 1 of the clinical trial will be when the central venous catheter is inserted. Total accrual of all participants is anticipated to take a total of 36 months.

### **3.6 PARTICIPANT WITHDRAWAL OR DISCONTINUATION**

Participants are free to withdraw consent and discontinue participation in the study at any time and without prejudice to further treatment.

If a participant withdraws consent, they will be specifically asked if they are withdrawing consent to:

- All further participation in the study including any further follow up
- Withdrawal of consent to the use of their study generated data
- Withdrawal to the use of any biological samples

No further participant contact should be made if the participant withdraws consent for participation in the study. Information about the reason(s) for discontinuation and collection of any new or ongoing AEs and medications should be collected at the time the participant withdraws consent.

For all other reasons for discontinuation from the study treatment phase, the participant should return to the clinic for the end of treatment (EOT) visit according to Section 6, Study Procedures/Evaluations And Schedule

#### **3.6.1 HANDLING PARTICIPANT WITHDRAWAL AND DISCONTINUATION**

Participants enrolled in this study that withdraw prior to receiving study drug will be replaced.

### **3.7 OFF-STUDY CRITERIA**

Criteria that can take a participant off-study include:

- Participant requests to be withdrawn from study without further follow-up,
- Participant is lost to follow-up,
- Participant completes study follow-up period,

- Death,
- Screen failure,
- Investigator's discretion

### 3.7.1 SCREEN FAILURES

Any participant that has signed the consent form but does not meet the study eligibility criteria, or meets study eligibility criteria but terminates their participation prior to receiving study treatment, will be considered a screen failure. The reason for screen failure should be captured in the database for each participant failing to meet the eligibility criteria.

## 3.8 STUDY DISCONTINUATION

This study may be temporarily suspended or prematurely terminated if there is sufficient reasonable cause. Written notification, documenting the reason for study suspension or termination, will be provided by the suspending or terminating party to IRB and manufacturer. If the study is prematurely terminated or suspended, the Investigator will promptly inform the IRB and the manufacturer and will provide the reason(s) for the termination or suspension.

Reasons for terminating the study may include the following:

- Incidence or severity of adverse events, in this or other studies, indicates a potential health hazard to participants.
- Data that are not sufficiently complete and/or evaluable.
- Investigators do not adhere to the study protocol, or applicable regulatory guidelines in conducting the study.
- Participant enrollment is unsatisfactory.
- Submission of knowingly false information from the study site to manufacturer or regulatory authorities.
- Upon instruction by local or other regulatory, or oversight authority.

Study may resume once concerns about safety, protocol compliance, data quality are addressed and satisfy the Sponsor/manufacturer, IRB and/or FDA.

## 4. INVESTIGATIONAL PRODUCT

A list of the adverse events and potential risks associated with the investigational or other agents administered in this study can be found in Section 7.4, Adverse Events.

### 4.1 XISOMAB 3G3

Xisomab 3G3 is a humanized IgG4 monoclonal antibody manufactured by Aronora, Inc. Refer to investigator brochure for additional details.

#### 4.1.1 ACQUISITION

Xisomab 3G3 will be supplied by the manufacturer, Aronora Inc., and prepared by the research pharmacy services at OHSU per manufacturer instructions. Following submission and approval of the required regulatory documents, a supply of xisomab 3G3 may be ordered from Aronora Inc. by completing a Drug Request Form.

#### 4.1.2 FORMULATION, APPEARANCE, PACKAGING AND LABELING

The 146 kDa antibody, xisomab 3G3, is produced as a lyophilized cake that is formulated in 8% sucrose, 10 mM histidine, 30 mM arginine HCl, 10 mM methionine, 80 ppm polysorbate 80, and has a pH of ~5.2 after reconstitution for intravenous administration. Xisomab 3G3 is packaged in a 10 mL nominal-volume USP-Type I colorless glass vial, stoppered with a bromobutyl rubber stopper and capped with an aluminum overseal with a flip-off cap. Vials containing xisomab 3G3 will denote drug product as being intended for investigation only. The lyophilized cake white is slightly yellow, clear and colorless liquid upon reconstitution.

#### 4.1.3 PRODUCT STORAGE AND STABILITY

The lyophilized xisomab 3G3 drug product should be stored upright at 2°C to 8°C. The drug product is stable for 36 months if stored at these conditions. Exposure to bright light should be avoided; standard room illumination does not necessitate any precautions. Once reconstituted, xisomab 3G3 is stable for at least 6 hours when stored at 25°C.

#### 4.1.4 COMPATIBILITY

Lyophilized xisomab 3G3 should be reconstituted in sterile water for injection.

#### 4.1.5 HANDLING

Aseptic technique, use of sterile disposable gloves and hand hygiene according to institutional standards. Manufacturer recommends disinfection of the septum of the injection stoppers using a swab with an appropriate disinfectant (based on ethanol or isopropanol).

#### 4.1.6 PREPARATION

Per manufacturer instructions, lyophilized xisomab 3G3 should be reconstituted with 2.6 ml sterile water for injection by carefully dispensing diluent into the vial of lyophilizate, trying to maintain the product and liquid in the base of the vial to avoid having the powder distribute around the walls of the vial. Gently swirl the vial content until the lyophilized drug product is completely dissolved and the solution is homogenous and transparent (not cloudy) when held against light. The final volume should result in 2.8 mL of reconstituted xisomab 3G3 antibody

drug product for administration. The final nominal concentration of xisomab 3G3 following reconstitution is 15 mg/mL. Multiple doses may be administered from one drug product vial.

#### 4.1.7 ADMINISTRATION

The reconstituted drug product should be administered intravenously via a peripherally inserted IV line or via the catheter as a slow bolus (approximately 1 minute) within 48 hours of catheter placement (i.e. +/- 2 days).

#### 4.1.8 SPECIAL CONSIDERATIONS FOR ADMINISTRATION

Xisomab 3G3 is to be administered at a fixed dose of 2 mg/kg. The participant's weight should be measured prior to administration. To calculate the exact volume of concentrated solution needed for the dose, apply the following equation:

$$V_{dose}(mL) = \frac{[Dose (mg/kg) \times Body weight (kg)]}{15 (mg/mL)}$$

*Example: for a 70 kg patient dosed at 2 mg/kg, then:*

$$V_{dose}(mL) = \frac{\left[2 \left(\frac{mg}{kg}\right) \times 70 (kg)\right]}{15 \left(\frac{mg}{mL}\right)} = 9.3 \text{ ml xisomab 3G3}$$

To calculate the number of vials needed for the dose follow these steps:

$$\text{Participant dose (vials)} = \frac{V_{dose}(mL)}{2.8 \text{ mL}}$$

If result is obtained with decimals, it should be rounded up to the nearest upper unit

*Example: for a 70 kg patient dosed at 2 mg/kg, the calculated patient dose is 3.3 vials, then 4 vials should be used to obtain the volume of concentrated solution.*

#### 4.1.9 ACCOUNTABILITY

RPS will maintain a careful record of the inventory and disposition of the study agent. (See the [NCI Investigator's Handbook for Procedures for Drug Accountability and Storage](#)).

Responsibility for drug accountability at the study site rests with the Investigator; however, the Investigator may assign some of the drug accountability duties to an appropriate pharmacist or designee. Inventory and accountability records must be maintained and readily available for inspection by the study monitor and are open to inspection at any time by any applicable regulatory authorities or other oversight bodies.

The Investigator or designee will collect and retain all used, unused, and partially used containers of study medication until full accounting has been completed. The Investigator or designee must maintain records that document:

- Investigational product delivery to the study site.
- The inventory at the site.

- Use by each participant including unit counts from each supply dispensed.
- Return of investigational product to the Investigator or designee.
- Destruction or return of investigational product for final disposal.

These records should include dates, quantities, batch/serial numbers (if available), and the unique code numbers (if available) assigned to the investigational product and study participants.

The investigational product must be used only in accordance with the protocol. The Investigator will also maintain records adequately documenting that the participants were provided the correct study medication specified.

Completed accountability records will be archived by the site. At the completion of the study, the Investigator or designee will oversee shipment of any remaining study drug back to Aronora Inc. for destruction according to institutional standard operating procedures. If local procedures mandate site destruction of investigational supply, prior written approval must be obtained from Aronora Inc.

#### **4.1.10 DESTRUCTION AND RETURN**

At the end of the study unused supplies of study drug should be destroyed according to institutional policies. Drug supplies will be counted and reconciled in full at the site with all monitoring procedures complete before destruction. Destruction will be documented in the Drug Accountability Record Form.

## 5. TREATMENT PLAN

### 5.1 DOSAGE AND ADMINISTRATION

Treatment will be administered on an *out-patient* basis. Reported adverse events and potential risks are described in Section 7.4, Adverse Event List.

Regimen Description			
Agent	Dose	Route**	Schedule
Xisomab 3G3	2 mg/kg	IV (via catheter)	Single dose administered within 48 hours of catheter placement ( $\pm$ 2 days).

\*\*Study drug should be administered as a slow bolus (approximately 1 minute).

Enrolled participants will receive a single fixed dose of xisomab 3G3 (2 mg/kg) through a peripheral IV or the inserted catheter within 48 hours of catheter placement (i.e.  $\pm$  2 days). If Xisomab 3G3 is administered prior to D1 catheter placement, eligibility must be confirmed prior to study drug administration. Participants will be monitored for at least 1 hour on the day of xisomab 3G3 administration for adverse events. Participants not receiving study drug or catheter placement as scheduled, may be rescheduled if within allowable screening window (i.e., no more than 28 days from consent). Participants receiving study drug but have a delay in placement of the catheter beyond 48 hours from time of xisomab administration, will not be considered evaluable for efficacy analysis (per Section 8.1), but will be followed for xisomab 3G3-associated toxicities (per Section 6.7).

Two (2) days after participants receive study drug they may proceed to undergo planned anticancer therapy per standard of care. Administration of planned cancer-directed therapy may not occur earlier than 2 days from time of giving study drug. The type(s) and frequency of administration of anticancer drug(s) comprising the participants' anticancer treatment regimen is at the discretion of treating physician and should be recorded in the CRF.

Consistent with institutional standards, participants may at any time during the study receive a standard of care workup with an ultrasound if they develop symptoms the investigator (or treating physician) believes to be suggestive of CAT, including arm pain and swelling or erythema in the same arm as the catheter. In such cases, the participant may receive antithrombotic therapy, at the discretion of their treating physician, per institutional guidelines.

### 5.2 TREATMENT PERIOD

After administration of a single, fixed dose of xisomab 3G3 (2 mg/kg) within 48 hours of catheter placement (with this placement defining Day 1), participants will undergo an end of treatment visit on Day 14 ( $\pm$  4 days).

### 5.3 CONCOMITANT MEDICATION AND SUPPORTIVE CARE GUIDELINES

Medications required to treat AEs, treat cancer, manage cancer symptoms, concurrent diseases and supportive care agents, such as pain medications, anti-emetics and anti-diarrheals are allowed in general. The participant must be told to notify the investigational site about any new medications begun after the start of the study treatment. All medications or nutritional/herbal supplements known to interact with study agent should be excluded. Prohibited medications must be stopped within 2 weeks or 1 half life (whichever is shorter) of investigational agent

administration. If the medication or supplement cannot be discontinued or replaced, the subject should be excluded from this study. Each participant's medication and supplement profile should be reviewed by investigator and/or an oncology trained pharmacist to ensure compliance with this aspect of care. All medications known to interact with the study drug should be avoided after day 18.

### 5.3.1 INFECTION PROPHYLAXIS AND TREATMENT

In general, participants with a documented infectious complication should receive oral or IV antibiotics or other anti-infective agents as considered appropriate by the Investigator for a given infectious condition, according to standard institutional practice.

### 5.3.2 TRANSFUSIONS OF PLATELETS AND RED BLOOD CELLS (RBC)

Blood, plasma, platelet or red blood cell transfusions are permitted as medically necessary per institutional guidelines. The decision for platelet or red blood cell transfusions should be done in collaboration with study investigator and participant's treating physician. The occurrence of any transfusion occurring prior to end of treatment visit on Day 14 ( $\pm$  4 days) should be recorded in (e)CRF. Abnormal, clinically significant bleeding may be managed at the discretion of the physician. Antifibrinolytic agents such as tranexamic acid may be used in the event of major bleeding events, and bleeding refractory to this may be managed with recombinant factor VIIa (Novo7) or prothrombin complex concentrates, at the discretion of the treating physician and in consultation with study PI.

### 5.3.3 ANTI-PLATELET AGENTS AND ANTICOAGULANTS

Anti-platelet agents and anticoagulants are permitted only as medically necessary, in case of new thrombosis, and managed per institutional guidelines. Standard of care anticoagulation may be started at any time in conjunction with xisomab 3G3 if deemed warranted by the treating physician. Anti-platelet agents and/or anticoagulants may not be given prior to administration of xisomab 3G3. The decision regarding use of antithrombotics should be done in collaboration with study investigator and participant's treating physician. Participants should be carefully monitored for bleeding risks. The use of any anti-platelet agents or anticoagulants occurring prior to end of treatment visit should be recorded in (e)CRF.

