Key Exclusion Criteria	
 
• Concurrent participation in another therapeutic clinical trial
 
• Leukemia (lymphoma and myeloma may be included)
 
• <math>\leq 72</math> hours since major surgery
 
• Abnormal renal function defined by an eGFR <math>< 45</math> mL/min
 
• Abnormal hepatic function defined as LFTs (AST, ALT or Total Bilirubin) <math>>2</math>x the upper limit of normal or known Child-Pugh class B or C cirrhosis.
 
• Abnormal baseline coagulation profile: 
 
◦ INR <math>> 1.5</math> or aPTT prolonged.
 
 
 
• Prior history of intracranial hemorrhage
 
• Primary brain tumors or known brain metastasis
 

	

• Major extracranial bleed within the last 6 months where the cause has not been identified or treated

• Use of oral anticoagulation at enrollment

• Known bleeding diathesis

• At the discretion of the investigator, any other contraindication to anticoagulation therapy

• Previously documented hypersensitivity to either the drug or excipients

• Participant is pregnant or breastfeeding

• Participant is expected to receive chemotherapy associated with a 15% or higher incidence of grade 3-4 thrombocytopenia

• Allergy to heparin and heparin derivatives

• History of venous thromboembolism (VTE) within the last 3 months.

Investigational Product	Xisomab 3G3 (2 mg/kg) is a recombinant, humanized, monoclonal IgG4 antibody that functions as a contact activation inhibitor and an anticoagulant by binding FXI and preventing FXI activation by FXIIa.
Statistical Considerations	The basis for our sample size calculation is the assumption of a 60% incidence of ultrasound-confirmed CAT (symptomatic or screened) over 18 days post-catheter placement in historical controls, informed by prior studies of cancer patients with venous catheters. A sample size of 50 patients, accounting for a 4% efficacy analysis ineligibility rate, was calculated to provide 80% power to detect a 20 percentage point decreased incidence of CAT at a two-sided alpha level of 0.05.

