## 1. BACKGROUND INFORMATION AND SCIENTIFIC RATIONALE

### 1.1 OVERVIEW OF CATHETER-ASSOCIATED THROMBOSIS

Peripherally inserted central catheters (PICCs) and indwelling central catheters are commonly used in both hospitalized and ambulatory patients who require centrally acting, or chronic intravenous (IV) medications including vasoactive drugs, antibiotics and chemotherapy. PICC lines are inserted through the peripheral veins of the upper extremity with the end of the catheter positioned above the patient's right atrium (**Figure 1**). PICCs offer many conveniences including limiting the need for further venipuncture and easy bedside insertion and removal; however, they are associated with high rates of complications including occlusion and/or mis-positioning, infection, and most commonly thrombosis. Catheter use is exceedingly common in modern health care (Centers for Disease Control [CDC] data suggest approximately 30% of hospitalized medical patients have a central venous catheter placed), and at least 5 million central venous catheters are inserted in the US annually. As such, measures to decrease common complications would have a large patient impact.

[figure not shown]
**Figure 1.** Anatomic placement of peripherally inserted central venous catheter.

Source: Blausen Medical Communications.

Thrombosis complicates over half of PICC lines. Rates of screened thrombosis vary due to heterogeneity in patient population, catheter type, and anticoagulation use, but incidences between 50-60% are generally reported at 14 days post insertion, with one study reporting a 61% incidence at 12-14 days in patients not on anticoagulation, and another 72% at 14-28 days. While many of these thromboses remain occult, about 5-7% of patients will develop symptomatic thrombosis leading to patient morbidity, increased healthcare utilization and delays in medical care. Likewise, indwelling central venous catheters (ie, "Mediports", "Port-a-Cath", or "ports") are plagued by high rates of thrombosis. Rates of CAT up to 62% have been reported in cancer patients not on anticoagulation.

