#### **3.2 PARTICIPANT EXCLUSION CRITERIA**

An individual who meets any of the following criteria will be excluded from participation in this study:

1. Actively receiving treatment in another therapeutic clinical trial
2. Active acute leukemia (lymphoma and myeloma are allowed)
3. At time of enrollment, known contraindication to anticoagulation therapy, including:
  - a. Clinically significant active bleeding

- b. Individual is within 72 hours of major surgery
- c. Abnormal baseline coagulation tests, including INR > 1.5, or aPTT prolonged
- d. Abnormal renal function defined by an eGFR < 45 mL/min
- e. Abnormal hepatic function defined as LFTs (AST, ALT or Total Bilirubin) >2x the upper limit of normal or known Child-Pugh class B or C cirrhosis.
- f. Prior history of intracranial hemorrhage
- g. Primary brain tumors or known brain metastasis
- h. Major extracranial bleed within the last 6 months where the cause has not been identified or treated
- i. Known bleeding diathesis
- j. Use of therapeutic anticoagulation or anti-platelet agents for any indication at enrollment
- k. At the discretion of the investigator, any other contraindication to anticoagulation therapy
- l. Presence of a pediatric-sized PICC line
- m. Participant is expected to receive chemotherapy associated with a 15% or higher incidence of grade 3-4 thrombocytopenia within 14 days of receiving study drug.

4. Preexisting intravenous catheter, or indwelling spinal or epidural catheter, at time of enrollment that is intended to remain for the duration of study. Participants may remain eligible if existing catheter is to be removed before placement of a catheter for cancer directed therapy. Removal of existing catheter should occur at least 24 hours prior to PICC or indwelling catheter insertion.

5. Previously documented hypersensitivity to either the drug or excipients

6. Psychiatric illness/social situations, or any other condition, that in the opinion of the investigator, would limit compliance with study requirements

7. Participant is pregnant or breastfeeding, or expecting to conceive or father children within the projected duration of the trial, starting with the screening visit through 90 days after the last dose of trial treatment.

8. Participant is allergic to heparin or heparin derivatives.

9. Participants with a history of venous thromboembolism within the last 3 months.

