## 5.4 PRECAUTIONARY AND PROHIBITED MEDICATIONS, TREATMENTS, AND PROCEDURES

Antithrombotic agents (Warfarin, heparin products, direct oral anticoagulants) should be avoided while on study (except for standard of care heparin/tPA flushes if required for catheter maintenance/occlusion). Elective invasive procedures should be delayed until completion of the initial 18 day drug efficacy evaluation period.

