### 8.3 SAMPLE SIZE, POWER, ACCRUAL RATE AND STUDY DURATION

#### 8.3.1 SAMPLE SIZE AND POWER

Based on the central venous catheter thrombosis rates and other parameters (e.g., population type, thrombosis evaluation period) in prior studies, the sample size calculation makes the assumption of a 60% incidence of ultrasound-confirmed CAT (i.e., both symptomatic and asymptomatic) over 18 days post- catheter placement in cancer patients not treated with xisomab. A sample size of 50 participants, accounting for a 4% efficacy ineligibility rate, is sufficient to provide 80% power to detect a 20 percentage point reduction in the incidence of CAT at a two-sided  $\alpha$  of 0.05.

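### The rules on antithrombotic use in the 18-day efficacy window conflict, and the analysis does not say how to handle participants who start such drugs without confirmed CAT

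*Combined protocol and SAP*

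**What the plan says.** Four sections govern antithrombotic use after dosing.

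- **Section 5.3.3** opens by limiting anti-platelets and anticoagulants to medical need arising from a new thrombosis. Its next sentence reads: "Standard of care anticoagulation may be started at any time in conjunction with xisomab 3G3 if deemed warranted by the treating physician". It bars these drugs before the xisomab dose, asks that decisions be shared with the study investigator, and requires use before the end of treatment visit to be recorded in the case report form.
- **Section 5.4**: "Antithrombotic agents (Warfarin, heparin products, direct oral anticoagulants) should be avoided while on study", with one exception: "except for standard of care heparin/tPA flushes if required for catheter maintenance/occlusion".
- **Section 5.1** lets the treating physician give antithrombotic therapy to a participant worked up for symptoms that suggest CAT. It does not make this depend on a positive ultrasound.
- **Section 6.7** ends follow-up at Day 60, death or the start of off-study anticoagulation, whichever is first.

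At entry, Section 3.2 excludes "Use of therapeutic anticoagulation or anti-platelet agents for any indication at enrollment". That criterion applies at enrollment only.

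On analysis, the efficacy set in Section 8.1 requires a catheter, xisomab within 48 hours of placement, and at least one CAT assessment by Day 18. Section 8.2.2 reports the incidence of ultrasound-detected CAT in that set with a 95% CI. Section 8.4 imputes nothing. None of the three mentions antithrombotics started after dosing.

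Section 8.3.1 makes "the assumption of a 60% incidence of ultrasound-confirmed CAT" over 18 days, citing three studies. Section 1.1 gives "one study reporting a 61% incidence at 12-14 days in patients not on anticoagulation" and a rate of up to 62% with indwelling catheters in cancer patients, also not on anticoagulation. It gives a third rate, 72% at 14 to 28 days, without saying whether those patients were anticoagulated.

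**The concern.** The trial has one arm, so there is no concurrent control in which co-medication could balance out. Any effect of other antithrombotics on the CAT count goes into the comparison with 60%. If someone is anticoagulated for another reason, or on suspicion, and then scans clear, the plan treats that result exactly as it treats a clear scan on xisomab alone. A clot prevented by the other drug is credited to xisomab.

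This can happen even on a strict reading of the rules. Section 2.1 provides for treatment of thrombosis other than CAT found on imaging, so a clot away from the catheter is a permitted reason to anticoagulate a participant who has no CAT.

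Because the rules conflict, the amount of such use depends on which sentence a treating physician follows. Section 6.7 adds a second path: if follow-up stops when anticoagulation starts, the Day 14 scan may not be done, and the participant leaves the efficacy set. The plan does not say which path applies, and the two affect the estimate differently.

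**Working it through.** **1. The plan's own figure.** Inputs from the Synopsis and Section 8.3.1: 60% against 40%, that is "80% power to detect a 20 percentage point decreased incidence of CAT at a two-sided alpha level of 0.05", with 4% not evaluable. For one proportion by the normal approximation:

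n = [(1.960 × √(0.6 × 0.4) + 0.842 × √(0.4 × 0.6)) / 0.20]² = 47.09, rounded up to 48; 48 / 0.96 = 50.

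The stated 50 is reproduced, with 48 evaluable.

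**2. A success boundary.** Section 8.2.2 states no success rule, so one has to be derived. Take the largest CAT count whose lower-tail probability at 60% is at most 2.5%. With X ~ Binomial(48, 0.6), P(X ≤ 21) = 1.66% and P(X ≤ 22) = 3.28%. The boundary is 21 of 48.

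**3. Where each participant goes**, for systemic anticoagulant or anti-platelet therapy started after dosing:

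| Situation | Handling under 6.9, 8.1, 8.2.2 and 8.4 |
|---|---|
| CAT confirmed by ultrasound within 18 days, then treated | CAT event |
| Started without confirmed CAT; scan by Day 18 clear | Non-event in the efficacy set |
| Started without confirmed CAT; no scan by Day 18 | Outside the efficacy set, not imputed |

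Only the second and third rows are a problem. The second can favour xisomab. The documents do not show the direction of bias in the third.

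**4. Size of the second path.** Assume that xisomab has no effect, that background CAT risk is 60%, and that m of the 48 are anticoagulated before any CAT and then scanned. The CAT count is the sum of Binomial(48 − m, 0.6) and Binomial(m, 0.6 × RR), where RR is the effect of the other drug. The documents do not give m.

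Two values of RR give a range:
- RR = 3.7 / 6.8 = 0.544, from the meta-analysis in Section 1.1. That result is for prophylactic anticoagulation and symptomatic CAT only, so applying it to screened CAT is an assumption.
- RR = 0, complete prevention, as an upper bound.

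Apparent incidence = 0.6 × [1 − (m/48)(1 − RR)]. False success = P(total ≤ 21).

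| m | Apparent CAT, RR 0.544 | False success, RR 0.544 | Apparent CAT, RR 0 | False success, RR 0 |
|---|---|---|---|---|
| 0 | 60.0% | 1.7% | 60.0% | 1.7% |
| 2 | 58.9% | 2.4% | 57.5% | 3.4% |
| 3 | 58.3% | 2.9% | 56.2% | 4.8% |
| 4 | 57.7% | 3.4% | 55.0% | 6.7% |
| 5 | 57.2% | 4.0% | 53.8% | 9.1% |
| 10 | 54.3% | 8.8% | 47.5% | 33.0% |

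If the other drug does not affect CAT (RR = 1), the figure stays at 1.7% for every m.

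**The case against.** The strongest reply is that the protocol already limits the problem. Participants on therapeutic anticoagulants or anti-platelets at enrollment, or with VTE in the previous three months, are excluded, and neither drug class may be given before the dose. Suggestive symptoms lead to an ultrasound. The second sentence of 5.3.3 can be read as qualified by the first, so that it covers new thrombosis only. All of this makes m likely to be small, and with two or three such participants the effect is modest. That part stands. The narrow reading removes the tension inside 5.3.3, but not the conflict with 5.4, which has no exception for new thrombosis. It also supplies no analysis rule.

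A reader might infer more than the documents support:

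- *That everyone anticoagulated before the planned scan counts as CAT-free.* Not so. The footnotes to Section 6.9 count any ultrasound within 18 days of placement, so CAT that is confirmed and then treated is an event. Others may never be scanned.
- *That Section 5.3 sets a further antithrombotic rule.* The sentence "All medications known to interact with the study drug should be avoided after day 18" is odd beside the exclusion of interacting drugs earlier in that section. But it names no antithrombotic, and these drugs have their own sections.
- *That catheter tPA hides CAT.* Nothing in the documents says that intraluminal tPA clears a clot visible on duplex. Section 5.4 permits it for occlusion, and occlusion treated with tPA is already an exploratory endpoint.
- *That the whole benchmark is free of anticoagulation.* Section 1.1 says so of the 61% and 62% rates, not of the 72%. Section 8.3.1 describes the comparison population only as cancer patients not treated with xisomab.
- *That 9.1% is the expected error with five participants.* It assumes complete prevention and is an upper bound.

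**Conclusion.** The point holds in a limited form. Sections 5.1, 5.3.3 and 5.4 do not give one rule for antithrombotics between dosing and Day 18, and Section 6.7 leaves it open whether the scan is still done once anticoagulation starts. A participant treated without imaging-confirmed CAT becomes either an ordinary non-event or an exclusion, and no analysis shows how much this matters.

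With two to five such participants of 48, the false-success probability moves from 1.7% to between 2.4% and 9.1%. At RR 0.544 it takes three to pass the nominal 2.5% tail. Substantial harm needs about ten (8.8% to 33.0%). These figures rest on an assumed number of participants, a derived 21 of 48 boundary, no drug effect, a 60% background risk, and an RR that is either borrowed from symptomatic CAT or set to its extreme. The planned sample size of 50 is unaffected. This is an inexpensive improvement to the plan. It does not show that the primary analysis is invalid.

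**What to change.** 1. **Reconcile Sections 5.1, 5.3.3, 5.4 and 6.7** into one consistent statement on antithrombotic use from dosing to Day 18, and state whether the Day 14 scan is still done after anticoagulation starts. Which clinical rule applies is the sponsor's decision; this review takes no position on it.

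2. **Keep the primary analysis in Section 8.2.2 and pre-specify one sensitivity analysis, labelled as worst case.** In it, count as CAT every participant given systemic anticoagulant or anti-platelet therapy between dosing and scan without imaging-confirmed CAT. Include those left unscanned for that reason, who also join the denominator. Report how many participants are affected and whether the conclusion changes. As a hypothetical example, 19 CAT of 48 with three such participants who scanned clear would become 22 of 48, above the derived boundary.

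Do not count the flushes and tPA that Section 5.4 permits as CAT.

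**Cost.** Wording and one extra tabulation. Section 5.3.3 already requires anticoagulant and anti-platelet use before the end of treatment visit to be recorded. The downside is a deliberately conservative figure that may be less favourable to xisomab: it will also count some participants whose therapy had nothing to do with CAT. That is why it should stay a sensitivity analysis. It should be fixed before results are known, because in an open single-arm trial a choice made afterwards would carry little weight.
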